8.5.5.2 Sensitivity Analyses for CL201-Rollover Cohort

8.5.5.2.1 Negative Binomial Regression in CL201-Rollover Cohort

The comparison between pre- and post-UX007 MCE rates will also be performed using a negative binomial regression model, which accounts for different follow-up times, with the time that each subject stays in the study included as an offset in the model. This analytic model estimates the ratio of event rate of the post-UX007 treatment period over that of the pre-UX007 treatment period. The model can be performed using SAS GENMOD procedure where the REPEATED statement is used to account for the within patient comparison. Two-sided 95% confidence interval will be provided for the rate ratio along with the p-value.

8.5.5.2.2 Alternative Clinical Definitions of MCEs in CL201-Rollover Cohorts

Sensitivity analysis will be performed by using an alternative definition of MCEs in pre- and post-UX007 treatment periods for:

- Rhabdomyolysis MCEs alternatively defined as a patient having CK value ≥ 1000 (5 times the upper limit of normal)
- Hypoglycemia MCEs alternatively defined as a patient having glycemia < 3.89 mmol (recommended by the American Diabetes Association as a level for intervention required in diabetic patients)

8.5.5.3 Analyses of Non-MCE endpoints in CL201-Rollover Cohorts

The following efficacy endpoints will be analyzed for this analysis:

- ECHO variables: Ventricle size, EF, and SF
- Growth measurements

In these analyses, baseline will be shifted to the UX007 treatment baseline. Scheduled visits in UX007-CL201 will be converted to months and then aligned with UX007-CL202 visits. For example, Week 24 visit in UX007-CL201 is mapped to Month 5.5 visit. Assessments taken during the UX007-CL202 baseline visit or the last scheduled visit from study UX007-CL201 are mapped to Month 18 visit. For other visits in UX007-CL202, 18 months will be added to the visit number. For example, Month 6 visit in UX007-CL202 is mapped to Month 24 visit.

Summary statistics will be presented for ECHO variables (ventricle size, EF, and SF) and corresponding changes from UX007 treatment baseline by visit.

The same analysis methodology as described in Section 8.5.3.3 will be adopted for these integrated analyses of growth measurements.

8.6 Pharmacokinetics Analysis

PK data will be summarized based upon PK sub-study set.

Plasma levels of UX007 metabolites will be summarized using descriptive statistics. PK parameters such as area under the plasma concentration-time curve (AUC), time to maximum plasma concentration (T_{max}), maximum plasma concentration (C_{max}), and trough plasma concentration (C_{trough}) will be estimated using standard non-compartmental analysis for participating subjects when there are sufficient data points. Descriptive statistics will be provided for PK parameters for UX007 metabolites.

8.7 Safety Analysis

The safety analysis will be performed using the safety analysis set. The safety parameters will include adverse events (AEs) and clinical laboratory, vital sign, and electrocardiographic (ECG) parameters and other safety parameters.

8.7.1 Adverse Events

Adverse events will be coded by system organ class and preferred term using the Medical Dictionary for Regulatory Activities (MedDRA version 23.1). The severity of an AE will be based on Common Terminology Criteria for Adverse Events (CTCAE), Version 5.0. If an AE cannot be graded based on CTCAE, the investigator will assign a severity based on 1 = mild, 2 = moderate, 3 = severe, 4 = life threatening, and 5 = Death.

An AE (classified by preferred term) will be considered a treatment emergent adverse event (TEAE) if it occurred on or after the first dose of UX007 and was not present prior to the first dose or worsening in severity or frequency of a preexisting condition. AEs that started in UX007-CL201 and continued into UX007-CL202 will not be considered UX007-CL202 TEAE since the start date is prior to UX007-CL202 first dose.

The following subject incidence of AEs will be summarized:

- Summary of TEAEs
- TEAEs by SOC and PT (preferred term)
- Related TEAEs by SOC and PT
- Serious TEAEs by SOC and PT
- Serious Related TEAEs by SOC and PT
- Grade 3 or 4 TEAEs by SOC and PT
- Deaths by SOC and PT
- TEAEs leading to discontinuation of study treatment by SOC and PT
- TEAEs by PT
- TEAEs leading to dose reduction by SOC and PT
- TEAEs leading to treatment interruption by SOC and PT
- TEAEs by PT
- TEAEs in the GI SOC
- Related TEAEs in the GI SOC
- GI ADRs
- GI ADRs leading to treatment discontinuation

Hepatobiliary TEAEs (see Appendix 11.4) For those AEs that occurred more than once during the study, the maximum severity or highest grade causality will be used to summarize the subject incidence. Exposure-adjusted adverse event incidence rates will also be presented at the preferred term level.

The number and percent of subjects experiencing one or more TEAE by SOC and PT in order of descending frequency may be summarized by age, gender and subtype of FAOD

history depending on the sample size. The planned age categories are ‘0-1 year’, ‘>1-6 years’, ‘>6-18 years’ and ‘>18 years’ and some may be combined if their number of subjects is small.

In the overall summary of adverse events table, there will be separate summaries for Grade 3 and Grade 4 TEAEs.

Detailed subject listings for all AEs, serious TEAEs, AEs leading to the discontinuation of study, AEs leading to the discontinuation of treatment, and death TEAEs leading to dose reduction, and TEAEs leading to treatment interruption will also be generated.

8.7.1.1 Gastrointestinal Adverse Drug Reactions

Summaries of gastrointestinal adverse drug reactions (GI ADRs) will be prepared to within each cohort. GI ADRs include the following PTs: Diarrhea, Abdominal pain, Abdominal pain upper, Gastrointestinal pain, Abdominal discomfort, Abdominal distension, Vomiting, and Nausea.

Summaries to characterize the severity and outcome of GI ADRs will include the following:

- 1) incidence of subjects with at least one GI ADR,
- 2) incidence of GI ADRs leading to treatment discontinuation,
- 3) a frequency distribution of the number of GI ADRs per subject,
- 4) descriptive statistics (n, mean, standard deviation, standard error, median and first and 3rd quartiles) for the number of GI ADRs per subject,
- 5) the frequency GI ADRs by severity and seriousness grade
- 6) a frequency distribution of the outcome of the GI ADRs that were
 - a) Recovered/Resolved
 - b) Resolving/Recovering
 - c) Recovered/Resolved with Sequelae
 - d) Death
 - e) Not Resolved

Characterization of the time course of GI ADRs will be provided for:

- 1) Time to first GI ADR with
- 2) Frequency of GI ADRs by time categories
- 3) Number of Subjects with GI ADR by time categories
- 4) descriptive statistics by time categories for any GI ADR

The frequency distributions will the following categories: <= 8 Weeks, > 8 Weeks to <= 24 Weeks, > 24 Weeks to <= 48 Weeks, > 48 Weeks to <= 78 Weeks, > 78 Weeks to <= 102 Weeks, > 102 Weeks to <= 126 Weeks, > 126 Weeks to <= 150 Weeks, > 150 Weeks to <= 198 Weeks, > 198 Weeks to <= 222 Weeks, etc.

The duration of a treatment-emergent GI ADR that was resolved is defined as AE end date minus AE start date plus 1 day. The duration of a treatment-emergent GI ADR for GI events

that are ongoing is defined as data cutoff date minus AE start date plus 1 day. The duration of treatment-emergent GI ADRs will be categorized as follows: 1 Day, 2 to <= 3 Days, 4 to <= 7 Days, 8 to <= 14 Days, 15 to <= 28 Days, and > 28 Days. Descriptive statistics will be also be provided.

Kaplan-Meier curves will be provided by cohort for time to first treatment-emergent GI ADR which is defined as AE start date minus the first UX007 dose date in UX007-CL202 plus 1 day. For the Kaplan-Meier curves, subjects will be censored at the end of study date or the data cutoff date, whichever is earlier. Time to first GI ADR in a subject is determined by the first GI ADR with non-missing start date of the subject. For the Rollover cohort, only UX007-CL202 data will be used and time plotted will be in weeks since the start of UX007-CL202.

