5.21 Exposure-adjusted Adverse Event Incidence Rate

The exposure-adjusted adverse event incidence rate is defined as the total number of occurrences of an AE summed across all subjects in the group divided by the total observation time for AEs for subjects in that group. The observation time for each subject is the duration from study day 1 (i.e., first dose of UX007) till the end of study period 1 or the date of clinical cutoff, whichever occurs earlier. The total observation time for AEs is the sum of observation times for all subjects in that group.

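### The binned part of the GI ADR time course compares counts across intervals 8 to 48 weeks wide with no stated person-time, so a constant risk would look like a changing one

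*SAP*

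**What the plan says.** SAP 8.7.1.1 lists four items for the GI ADR time course: time to first GI ADR, "Frequency of GI ADRs by time categories", "Number of Subjects with GI ADR by time categories", and "descriptive statistics by time categories for any GI ADR". The categories are "<= 8 Weeks, > 8 Weeks to <= 24 Weeks, > 24 Weeks to <= 48 Weeks, > 48 Weeks to <= 78 Weeks", then "> 78 Weeks to <= 102 Weeks, > 102 Weeks to <= 126 Weeks, > 126 Weeks to <= 150 Weeks", then "> 150 Weeks to <= 198 Weeks, > 198 Weeks to <= 222 Weeks, etc". The summaries are made within cohort. The section names no number at risk, person-time or interval rate for these categories.

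Two related analyses do allow for follow-up:

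- The same section plans Kaplan-Meier curves by cohort for time to first GI ADR, censored at end of study or data cutoff.
- SAP 8.7.1 states: "Exposure-adjusted adverse event incidence rates will also be presented at the preferred term level". SAP 5.21 defines the denominator: "The observation time for each subject is the duration from study day 1" to the end of study period 1 or the cutoff, summed over subjects. It is one total per group and is not divided by time since first dose.

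Follow-up differs between subjects. SAP 3.3 allows up to 84 months, cut short by market approval, and subjects may terminate early. The Amendment 6 summary in the protocol shows that enrolment was still open in October 2019, so entry is staggered.

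**The concern.** A table of counts by time since first dose is read as a picture of risk over time. That reading works only if the intervals are comparable in width and in the number of subjects under observation. Here neither is assured.

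The purpose of these tables makes this matter. The SAP amendment summary says they were added to characterise the severity, outcome and time course of GI ADRs. Protocol 5.3 reports that in earlier UX007 trials the commonest GI events arose mainly while the dose was being raised. The natural question is whether the rate falls after that. The shortest bin sits where an early excess is expected, and the longest, at 150-198 weeks, sits among 24-week neighbours.

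**Working it through.** The documents give no expected count for these tables, so there is no figure to reproduce.

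**Inputs from the SAP.** The bin edges in 8.7.1.1 are 0, 8, 24, 48, 78, 102, 126, 150, 198 and 222 weeks. The widths are their differences. Weeks per year = 365.25 / 7 = 52.18 (day conversions in SAP 5.5).

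**Assumptions, not from the documents.** N = 100 subjects as a scaling base; a constant rate of 1.0 GI ADR per person-year; and several follow-up patterns S(t), the fraction of subjects still observed at week t.

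**Formulas.**
- Expected events in bin j = N × rate × (integral of S(t) over the bin) / 52.18.
- Expected subjects with at least one event in bin j, with full follow-up = N × (1 − exp(−rate × width / 52.18)).

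**Example, full follow-up.** Weeks 0-8: 100 × 1.0 × 8 / 52.18 = 15.3. Weeks 150-198: 100 × 1.0 × 48 / 52.18 = 92.0. The ratio is 48 / 8 = 6.0, whatever the rate.

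**Expected events per bin at constant risk, and subjects with at least one event (last column).**

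| Weeks | Width | Full follow-up | 10%/yr loss | 20%/yr loss | Follow-up uniform 52-260 wk | Follow-up uniform 0-222 wk | Subjects, full follow-up |
|---|---|---|---|---|---|---|---|
| 0-8 | 8 | 15.3 | 15.2 | 15.1 | 15.3 | 15.1 | 14.2 |
| 8-24 | 16 | 30.7 | 29.7 | 28.6 | 30.7 | 28.5 | 26.4 |
| 24-48 | 24 | 46.0 | 42.8 | 39.4 | 46.0 | 38.5 | 36.9 |
| 48-78 | 30 | 57.5 | 50.6 | 43.9 | 54.4 | 41.2 | 43.7 |
| 78-102 | 24 | 46.0 | 38.4 | 31.3 | 37.6 | 27.3 | 36.9 |
| 102-126 | 24 | 46.0 | 36.5 | 28.3 | 32.3 | 22.4 | 36.9 |
| 126-150 | 24 | 46.0 | 34.8 | 25.5 | 27.0 | 17.4 | 36.9 |
| 150-198 | 48 | 92.0 | 64.8 | 43.8 | 38.0 | 19.9 | 60.1 |
| 198-222 | 24 | 46.0 | 30.1 | 18.7 | 11.1 | 2.5 | 36.9 |
| Largest/smallest (unrounded) | 6.0 | 6.0 | 4.3 | 2.9 | 4.9 | 16.6 | 4.2 |

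The full follow-up column is the ratio 1 : 2 : 3 : 3.75 : 3 : 3 : 3 : 6 : 3. In every pattern the counts rise to weeks 48-78 and bump up again at 150-198, although risk never changes. The steady decline after week 78 appears only in the columns with lost follow-up.

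**The converse.** Let the true rate be 3.0 per person-year in weeks 0-8 and 0.5 afterwards, with full follow-up. Weeks 0-8: 100 × 3.0 × 8 / 52.18 = 46.0. Weeks 150-198: 100 × 0.5 × 48 / 52.18 = 46.0. A six-fold early excess gives the same count in both bins.

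**After correction.** Dividing expected events by person-years in each bin returns 1.00 per person-year in all nine bins, under every pattern in the table.

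**The case against.** The strongest reply is that the section already contains a proper risk-set analysis. The Kaplan-Meier curve does not depend on bin width and allows for censoring. This stands for the first GI ADR. A reader might infer from the binned tables that the whole GI ADR time course is unadjusted; the documents do not support that. The curve says nothing, however, about second and later events or about burden in later intervals.

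Second, the SAP is silent on denominators and does not rule them out. The table list is in a separate document (SAP 9), and SAP 8.1 has categorical variables summarised by number and percentage of subjects. The silence is fairly noted. But a percentage of subjects does not correct for width: the last column of the table, read as percentages, still runs from 14.2 to 60.1 at constant risk.

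Third, the widths are printed, so a reader can divide by them, and narrow early bins are sensible if GI events cluster early. On width alone they understate an early excess, so one that showed in the counts would be real. It would therefore be too strong to say that the tables can never reveal a decline. But loss of follow-up pulls the other way, and without person-time a reader cannot separate the two effects.

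Fourth, the 48-week bin may simply lack a 174-week cut-point. That is plausible. Splitting it removes the late bump, but the widths still range from 8 to 30 weeks, a ratio of 3.75.

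Finally, these are untested descriptive summaries, and all AEs are listed by subject. That limits the consequence.

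**Conclusion.** The point holds for the binned event and subject counts in SAP 8.7.1.1. The six-fold spread in expected event counts needs only a constant rate and full follow-up. The further distortion from unequal follow-up is certain in kind but unknown in size: over the assumed patterns the largest-to-smallest ratio runs from 2.9 to 16.6. A reader might infer that the late counts must show a spurious decline in risk. That depends on the loss of follow-up, which the documents do not quantify.

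Neither related analysis closes the gap, since one stops at the first event and the other is a whole-period rate by preferred term. The issue concerns a descriptive safety summary. It does not touch the primary efficacy endpoint, the primary safety endpoint or any decision rule, but the change is worth making before the tables are produced.

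**What to change.** In SAP 8.7.1.1, for each time category and cohort, report beside the counts:

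- the number of subjects at risk at the start of the interval;
- person-years in the interval, using the SAP 5.21 observation window cut at the bin edges;
- GI ADRs per person-year with a 95% confidence interval that allows for repeated events in the same subject.

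Split weeks 150-198 into 150-174 and 174-198, and write out the categories now covered by etc. If proportions of subjects are shown, give the number at risk and add a note that they should not be compared across bins of different width.

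The cost is a denominator and a rate column in planned tables. The dates needed are already collected. Rates in late bins may be imprecise within a cohort, and the confidence intervals will show that.

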In clinical trials with UX007, the most common treatment-related treatment-emergent adverse events (TEAEs) were gastrointestinal (GI) in nature. Of these most frequently reported TEAEs were diarrhea and abdominal pain, which were mild or moderate in severity, and mostly occurred during up-titration of the initial dose of triheptanoin, and lasted a median duration of 3 days. Where it was deemed clinically necessary in the judgment of the Investigator, treatment-related GI events may be managed with UX007 dose reductions. The adverse drug reactions for triheptanoin in subjects with LC-FAOD are diarrhea, abdominal pain (including preferred terms of abdominal pain, abdominal pain upper, abdominal discomfort, abdominal distention, and gastrointestinal pain), vomiting and nausea.

Overall the risk-benefit ratio of triheptanoin/UX007 appears to be favorable based on the safety record to date and the benefit observed in published observational studies, compassionate use programs, and Ultragenyx clinical trials.

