7.2.3 Missing Date Imputation for Adverse Events and Concomitant Medications

The following conventions will be used to impute missing portions of dates for adverse events and concomitant medications. Note that the imputed values outlined here may not always provide the most conservative date.

Missing Start Dates

- If the day is unknown, then:
 - If the month and year match the first dose of investigational product start date month and year in this study, then impute the day of the first dose date.
 - Otherwise, assign the first day of the month.
- If the month is unknown, then:
 - If the year matches the year of the first dose of investigational product date in this study, then impute the month and day of the first dose date in this study.
 - Otherwise, assign 'January'
- If the year is unknown, then the date will not be imputed and will be assigned a missing value.

If the imputed date is earlier than birth date, then birth date will be used. If the imputed start date is later than the end date, then the start date will be set as the same date as the end date.

Missing Stop Dates (not applicable to ongoing)

- If the day is unknown, then assign the last day of the month.
- If the month is unknown, then assign 'December.'
- If the year is unknown, then the date will not be imputed and will be assigned a missing value, and the event will be considered ongoing. If the AE has been recorded as resolved/recovered, all efforts should be made to obtain the date from the Investigator.
- If the resulting end date is after the date of study completion / discontinuation/ data cutoff, set the imputed end date as close to the date of study completion / discontinuation/ data cutoff as possible without overwritten existing information.

If the year is missing for the start date and the stop date (observed or imputed) is on or after the first dose or event is ongoing, the start date will be imputed as the first dose date.

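### Read together, SAP 7.2.3 and 8.7.1.1 compute GI ADR duration from imputed dates, which lengthens partial-date events and can run an event recorded as resolved to the data cutoff

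*SAP*

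**What the plan says.** SAP 8.7.1.1 gives two duration formulas. For resolved events: "The duration of a treatment-emergent GI ADR that was resolved is defined as AE end date minus AE start date plus 1 day". For GI events "that are ongoing is defined as data cutoff date minus AE start date plus 1 day", the end point is the cutoff and not the subject's own last visit. Durations are then grouped, with 15 to 28 days and over 28 days as the top two categories, and descriptive statistics are added. The same section tabulates outcome, including resolved and not resolved.

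SAP 7.2.3 sets the date rules: "The following conventions will be used to impute missing portions of dates for adverse events and concomitant medications". The relevant ones are:

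- **Start day missing.** "If the month and year match the first dose of investigational product start date month and year in this study", the first dose date is used. If not: "Otherwise, assign the first day of the month".
- **Start month missing.** January is used, or the first dose date if the year is the first-dose year.
- **Stop day missing.** "If the day is unknown, then assign the last day of the month".
- **Stop month missing.** December is used.
- **Stop year missing.** The date "will be assigned a missing value, and the event will be considered ongoing". If the event is recorded as resolved, the site is to be asked for the date. Nothing is said about what happens if the query fails.

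Imputed stop dates that fall after study completion, discontinuation or cutoff are pulled back to about that date. SAP 7.2 keeps imputed values out of listings, but no text keeps them out of the duration table. Protocol 5.3 reports that the commonest GI events in earlier UX007 trials "lasted a median duration of 3 days" and mostly occurred during up-titration.

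**The concern.** Placing starts early and stops late is a reasonable convention for deciding whether an event is treatment-emergent. It is a poor one for measuring length, because subtracting an early start from a late stop moves the result one way only. When typical events last about 3 days, a single month of rounding is about ten times the quantity being measured.

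The unknown-stop-year rule is a different problem. It can classify an event known to have ended as ongoing, so two tables in the same section would disagree about that event.

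The SAP 2.0 summary of changes says these GI summaries were added for in-depth analysis of adverse drug reactions. The over-28-days category is where a reader would look for persistent GI toxicity, and it is the category most exposed.

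**Working it through.** The documents give no figure to reproduce, so the check applies the two sections' rules by date arithmetic.

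**Inputs.** True duration is 3 days (Protocol 5.3 median). Formulas and imputation rules are from SAP 8.7.1.1 and 7.2.3. Assumed: start dates spread evenly over a four-year calendar (1,461 days); 1 January or 31 December when the month is missing; the end-of-study cap does not bind.

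**Two hand checks.**
- Start and stop both recorded only as March 2017: 31 − 1 + 1 = 31 days.
- Start 5 January 2017, stop recorded only as 2017: day 365 − day 5 + 1 = 361 days.

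**A true 3-day event under each pattern.**

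| Missing | Computed duration (days) | Over 28 days |
|---|---|---|
| Stop day only, or start day only outside the first-dose month | mean 17.7, range 3–33 | 14.6% |
| Both days, same month, outside the first-dose month | mean 30.5, range 28–31 | 94% |
| Both days, event within the first-dose month | mean 16.7, range 3–31 | 8.6% |
| Stop month only | mean 185, range 3–368 | 93% |
| Both months, same year, outside the first-dose year | 365–366 | 100% |
| Stop year, query failed, treated as ongoing | 366, 731, 1,827 or 2,558 if cutoff is 1, 2, 5 or 7 years after start | 100% |

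**Effect on the mean**, with a share p of events affected and all others at 3 days: mean = (1 − p) × 3 + p × d.
- Both days missing, p = 5%: 0.95 × 3 + 0.05 × 30.5 = 4.4 days.
- One day missing, p = 5%: 0.95 × 3 + 0.05 × 17.7 = 3.7 days.
- Stop year unknown with cutoff 2 years later, p = 2%: 0.98 × 3 + 0.02 × 731 = 17.6 days. At p = 5%: 39.4 days.

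**Effect on the over-28-days category.** This needs an assumed spread of true durations. The simulation used a lognormal with median 3 days, with 5% of events lacking a day (half stop day only, half both days) and no first-dose exception.

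| Assumed log-SD | Truly over 28 days | Tabulated over 28 days | Artefact as share of category |
|---|---|---|---|
| 0.9 | 0.6% | 3.4% | 82% |
| 1.3 | 4.1% | 6.9% | 40% |
| 1.75 | 10.0% | 12.6% | 21% |

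In all three rows the mean rises by about 1.1 days (for example 4.5 to 5.6 at log-SD 0.9) and the median stays at 3. With 20% of events lacking a day, the median moves to 4 or 5.

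**The case against.** The strongest reply has five parts.

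- **The link is inferred.** Section 8.7.1.1 never says that its dates are imputed ones. That is true. It remains the default reading, because 7.2.3 covers all adverse-event dates, imputed values are barred only from listings, and both sections use the ongoing status. Two programmers could still produce different tables.
- **The unknown stop year is a residual case.** The SAP first requires a query, and the schedule of events has a contact about every 3 months at which AEs are reviewed, which should usually bound the stop date. This stands. If the query fails, the event could be argued to fall under the resolved formula. That formula cannot be evaluated without an end date, so only the ongoing one yields a number.
- **The first-dose exception softens the effect.** This also stands. Events in the first-dose month are stretched less (mean 16.7 against 30.5 days), and Protocol 5.3 places most GI events in up-titration. It helps mainly naïve subjects, for whom first dose in this study is the start of treatment.
- **The bias is cautious.** It overstates GI toxicity in one untested descriptive table, and the listings still show the recorded dates. This lowers the priority but does not make the durations right.
- **Dropping partial dates has its own bias.** Prolonged events may have vaguer dates. This stands, and it is why the fix includes a sensitivity table.

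**Conclusion.** The point holds as a minor one. Applied as written, the stated rules lengthen partial-date GI ADRs. They can also give an event recorded as resolved a duration running to the cutoff while the outcome table counts it as resolved. The exposed outputs are the mean and the over-28-days category. The median is robust if few dates are partial. The fault is confined to the duration summary; other GI ADR summaries, AE incidence and MCE results do not use these durations.

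A reader might infer that every partial date produces a month- or year-long event. It does not. A month-long result for a short event generally needs both days missing outside the first-dose month, and a result of many months or more needs a missing month or stop year.

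A reader might also infer that the mean and the top category would largely reflect date completeness. The documents do not support that. They give neither the share of partial dates nor the spread of true durations. At 5% missing days the artefact is between about a fifth and four fifths of the top category, depending on the assumed spread. In the same example at log-SD 0.9, it adds only 1.1 days to a mean of 4.5. The mean is dominated only if some stop months or years are missing.

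**What to change.** In SAP 8.7.1.1:

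1. Tabulate duration for GI ADRs with complete recorded start and stop dates. Show truly ongoing events separately, and report the number of events with partial dates.
2. State that the ongoing formula does not apply to an event recorded as resolved. If its stop year stays unknown after the query, its duration is missing.
3. Add one sensitivity table as an upper bound, using either the 7.2.3 imputed dates or the first contact at which resolution was reported. This guards against selective loss of longer events.

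Leave the 7.2.3 imputed start dates in place for treatment-emergence, time to first GI ADR and the time categories. Confining them to treatment-emergence alone would go too far, since the other two also need start dates.

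The cost is a few sentences, an imputed-date flag, one extra table and a slightly smaller n in the main duration table.
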